#### **7.1.7. Additional Analysis of Adverse Events**

##### **7.1.7.1. Study Drug Related Injection Site Reactions**

Additional analysis of AEs will be performed for injection site reaction (ISR) related to study drug, which is defined as an AE related to study drug with HLT of “Injection Site Reactions”. The following summaries will be provided for each SC injection (eg, Day 1 SC, Week 26, and Week 52) and the overall using All LEN Analysis.

- Number of participants that received SC injection
- Number and percentage of participants with study drug related ISRs
- Number and percentage of participants with study drug related ISRs by grade
- Number and percentage of participants with study drug related ISRs by PT term

The denominator for the percentage calculation for the by visit summary and the overall summary will be based on the total number of participants who receive at least 1 SC injection at the visit of interest and the total number of participants who receive at least 1 SC injection at any injection visit, respectively.

Duration of the ISR will also be calculated and summarized. Duration for a given event is defined as the ISR stop date minus the ISR onset date plus 1 day. For ISR with ongoing stop date, stop date will be imputed as last study date or data cut date, whichever is the earliest. Duration of ISR events in days will be summarized using descriptive statistics.

A by-participant listing for study drug related ISRs and the corresponding duration will be provided.

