Text has been updated to add more information regarding timing of reporting of serious adverse events (SAEs) and initial SAE reporting to align with internal processes.	Section 7.3.2.1

Rationale for Key Changes Included in Amendment 5	Affected Sections
Section describing management of injection site reactions (ISRs) that are Grade 3 or higher, or persisting for more than 26 weeks has been removed. The additional assessments and extended monitoring criteria described in this section were added to assess the risk of ISRs in participants who were exposed to subcutaneous lenacapavir administered from borosilicate vial lots. This section is deleted as use of borosilicate vials has been discontinued and adequate safety data to assess the risk of ISRs has been collected from the study to date. Additionally, currently there are only 13 participants remaining on the study.	Section 7.6.4
The section describing the safety monitoring committee has been removed because it is no longer applicable to the study. There are no additional meetings planned for the safety monitoring committee.	Section 7.8
Text describing the availability of study results on ClinicalTrials.gov has been added to align with new International Council for Harmonisation (ICH) guidance.	Section 9.2.2
A new section describing data protection has been added to align with new ICH guidance.	Section 9.3.5
Recommendations for phone contact with participants after Week 156 to follow up on AEs has been added.	Appendix 2
Minor changes to correct typographic errors.	Throughout, as needed

Amendment 4 (18 January 2023)

Rationale for Key Changes Included in Amendment 4	Affected Sections
Long-term data collection were added to support that lenacapavir in combination with optimized background regimen at Weeks 104 and 156 (from the first subcutaneous [SC] dose of GS-6207) have sustained durable virologic responses, clinically meaningful improvement in CD4+, and was well tolerated in people living with human immunodeficiency virus with multidrug resistance and limited options. Secondary objectives and endpoints have been added to reflect this long-term data collection. To reflect the long-term data collection window, Year 2 and 3 analyses have been added to the Week 104 and 156 analysis window.	Synopsis, Study Design Schema, Sections 2, 3, 5.5, 8, 8.2.3, and 8.2.4

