### **2.1.5. Year 2 Analysis**

The Year 2 Analysis will be performed after all participants in both cohorts have had HIV-1 RNA data in the Week 104 analysis window (or reached the upper limit of the analysis window with missing HIV-1 RNA data), or have prematurely discontinued or completed the study drug, outstanding data queries have been resolved or adjudicated as unresolvable, and the data have been cleaned and finalized.

This SAP describes the analysis plan for the Year 2 Analysis.

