### **2.1.6. Year 3 Analysis**

The Year 3 Analysis will be performed after all participants in both cohorts have had HIV-1 RNA data in the Week 156 analysis window (or reached the upper limit of the analysis window with missing HIV-1 RNA data), or have prematurely discontinued or completed the study drug, outstanding data queries have been resolved or adjudicated as unresolvable, and the data have been cleaned and finalized.

This SAP describes the analysis plan for the Year 3 Analysis.

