#### **6.2.1. US FDA-defined Snapshot Algorithm**

The analysis window at Week 104 is defined as from Study Day 688 to Study Day 778, inclusive, where Study Day is calculated from the first dose of oral LEN. Participants who have missing HIV-1 RNA at Week 104 and have completed the study before reaching the upper limit of the analysis window for Week 104 will be excluded. All HIV-1 RNA data collected on-treatment will be used in the snapshot algorithm.

HIV-1 RNA on-SC-LEN-treatment is defined as HIV-1 RNA collected up to 28 weeks from the last SC LEN, and on or prior to the first dose of oral bridging of LEN or up to 28 weeks from any resumed SC LEN after oral bridging for participants who received oral bridging of LEN.

HIV-1 RNA on-oral-LEN-treatment is defined as HIV-1 RNA collected after the First Dose Date of Oral Bridging or oral reload after the first SC LEN, and up to 7 days from the Last Dose Date of Oral Bridging for participants who discontinued from the oral bridging of LEN, or up to minimal (Last Dose Date of Oral Bridging +7, First Dose Date of Resumed SC Injection) for participants who resumed SC LEN.

For the snapshot algorithm, HIV-1 RNA on-SC-LEN-treatment will be used. If there is no such result, HIV-1 RNA on-oral-LEN-treatment will be used.

Virologic outcome will be defined as the following categories:

- HIV-1 RNA < 50 copies/mL: this includes participants who have the last available on-treatment HIV-1 RNA < 50 copies/mL in the Week 104 analysis window
- HIV-1 RNA  $\geq$  50 copies/mL: this includes participants
  - Who have the last available on-treatment HIV-1 RNA  $\geq$  50 copies/mL in the Week 104 analysis window, or
  - Who do not have on-treatment HIV-1 RNA data in the Week 104 analysis window and
    - Who discontinue study drug prior to or in the Week 104 analysis window due to lack of efficacy, or
    - Who discontinue study drug prior to or in the Week 104 analysis window due to reasons other than AE, death, or lack of efficacy and have the last available on-treatment HIV-1 RNA  $\geq$  50 copies/mL
- No Virologic Data in the Week 104 analysis window: this includes participants who do not have on-treatment HIV-1 RNA data in the Week 104 analysis window because of the following:
  - Discontinuation of study drug prior to or in the Week 104 analysis window due to AE or death (regardless of whether the last available on-treatment HIV-1 RNA < 50 copies/mL or not) or,

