#### 7.1.7.2. Selected Study Drug Related ISRs

Selected study drug related ISRs include study drug related injection site induration, nodule, swelling, erythema, and pain.

The number and percentage of participants who experienced at least 1 selected study drug related ISR will be provided and summarized by SOC, PT and severity for each SC injection and the overall.

For each PT term of the study drug related ISRs, percentage of ongoing and resolved events will be summarized for each SC injection (Day 1 SC, Week 26, Week 52, etc.) and the overall at both participant-level and event-level.

For the participant-level summary, if a participant had more than one events of the same PT term, the participant will be counted in the “Ongoing” category unless all events of that same PT term have been resolved.

For the event-level summary, duration of the resolved events will also be summarized using descriptive statistics.

A by-participant listing for study drug related injection site induration and nodules and the corresponding duration will be provided.

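### Ongoing injection site reactions are summarised as if finished in SAP 7.1.7.1 and left out of the durations in 7.1.7.2, so the mean and the resolved-only durations run low for long-lasting reactions

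*SAP*

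**What the plan says.** SAP 7.1.7.1 takes ISR duration as stop date minus onset date plus one day. For events that have not ended it adds: "For ISR with ongoing stop date, stop date will be imputed as last study date or data cut date, whichever is the earliest". Then: "Duration of ISR events in days will be summarized using descriptive statistics". SAP section 3 (General Analysis Approaches) defines those statistics to include the mean, median, Q1 and Q3. Nothing in 7.1.7.1 separates imputed from observed durations.

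SAP 7.1.7.2 plans a second summary: "For each PT term of the study drug related ISRs, percentage of ongoing and resolved events will be summarized for each SC injection", and overall, at participant and event level. It continues: "For the event-level summary, duration of the resolved events will also be summarized using descriptive statistics". The natural reading is that resolved-only duration belongs to that event-level table, so it is by PT, per injection and overall. By-participant listings of duration are planned in both sections.

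On timing, SAP 2.1.5 states: "The Year 2 Analysis will be performed after all participants in both cohorts have had HIV-1 RNA data in the Week 104 analysis window" (or have passed its upper limit, or have stopped or completed study drug). SAP 6.2.1 gives the window: "The analysis window at Week 104 is defined as from Study Day 688 to Study Day 778, inclusive". SAP 2.1.6 sets a parallel trigger for Year 3 at Week 156. Neither the SAP nor the protocol plans a Kaplan-Meier or other censoring-aware estimate of ISR duration.

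**The concern.** An ongoing ISR has a known minimum duration, not a known duration. Treating the minimum as the duration pulls the mean down. Dropping ongoing events, as the second summary does, keeps the short ones and loses the long ones.

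Injections are 26 weeks apart and the data are cut at one time, so each later injection has less follow-up. In a table by injection, resolved-only durations of a long-lasting reaction such as a nodule or induration would shorten from one injection to the next for that reason alone. A reader could take this for improving tolerability. Duration of induration and nodules has its own listing in 7.1.7.2, so the plan itself treats it as worth reporting.

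**Working it through.** **Direction (no distribution needed).** Let D be the true duration and C the time from onset to the imputed stop date.
- The 7.1.7.1 value is min(D, C), which never exceeds D. Its mean is below the true mean as soon as one ongoing ISR outlasts its imputed date. Last study date (SAP 3.8.1) is an actual visit, laboratory or AE date, so it can precede the data cut and shorten C further.
- The 7.1.7.2 value estimates D given D ≤ C, whose mean cannot exceed that of D.
- Small example: nine ISRs resolve at 10 days and one, ongoing at 200 days, truly lasts 400. True mean (90 + 400)/10 = 49; imputed mean (90 + 200)/10 = 29; resolved-only mean 10.

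**Inputs for size.** The plan has no duration figure to reproduce.
- From the SAP: injections on nominal Study Days 15, 197, 379, 561 and 743 (Day 1 SC, Weeks 26, 52, 78, 104).
- Assumed: onset 3 days after injection; exponential durations; equal reaction rates at each injection; no dropout; data cut, in study days, uniform over 778 to 1142.
- Follow-up = cut day − injection day − 3. At Day 778: 760, 578, 396, 214 and 32 days. At Day 688, the earliest day in the window: 670, 488, 306 and 124 days for the first four.

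**Pooled over five injections (300,000 simulated participants per scenario).**

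| Assumed true median | Imputed median | Resolved-only median | Imputed mean low by |
|---|---|---|---|
| 30 | 30 | 30 | 1% |
| 90 | 86 | 82 | 7% |
| 180 | 161 | 140 | 18% |
| 365 | 271 | 203 | 38% |

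At a true median of 180, Q3 is 361 true against 303 imputed. Kaplan-Meier, censoring ongoing events, returned 30, 90, 180 and 365.

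**By injection, true median 180.**

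| | Day 1 SC | Wk 26 | Wk 52 | Wk 78 | Wk 104 |
|---|---|---|---|---|---|
| Resolved-only median | 173 | 166 | 151 | 126 | 83 |
| Imputed median | 180 | 181 | 180 | 180 | 113 |
| Percent ongoing | 3 | 6 | 12 | 24 | 48 |

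Cross-check: for exponential durations the shortfall in the imputed mean equals the share ongoing. (3 + 6 + 12 + 24 + 48)/5 = 18.6%, which matches 18% given rounding.

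**Share lasting past 26 weeks (182 days), true median 180.** True share = 2^(−182/180) = 0.496. Where C > 182, min(D, C) exceeds 182 exactly when D does, so the first four injections are classified correctly. For Week 104, C is uniform over 32 to 396, so P(C > 182) = (396 − 182)/364 = 0.588, and the apparent share is 0.588 × 0.496 = 0.292. Pooled: (4 × 0.496 + 0.292)/5 = 0.455 against 0.496.

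**Other assumptions (true median 180 unless stated).**
- Cuts over 688 to 1142: imputed 157, resolved-only 137, mean 20% low.
- Reaction rate falling to 60% at each injection: 175, 158, 9%.
- Weibull shape 0.7: 154, 103, 39%.
- 80% short reactions (median 7) and 20% long (median 180): median 10 true and 10 imputed; mean 60 true, 51 imputed.
- Year 3-type cuts (1142 to 1506, assumed), seven injections: 166, 151, 13%. The first five injections largely recover; Weeks 130 and 156 then show resolved-only medians of 125 and 83.
- One cut for everyone at Day 778, onset on the injection day, true median 125: imputed 85, resolved-only 98, Kaplan-Meier 125. Here the order of the two planned medians reverses; both remain low.

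**The case against.** Four objections have force.

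**Persistence past 26 weeks.** A reader might infer that the planned durations cannot show what share of ISRs lasts past 26 weeks. The documents do not support that. Even with a Day 688 cut, the first three injections have 306 days of follow-up or more, so barring earlier study exit their events are classified correctly and can be counted from the listings. The share is understated only when injections with shorter follow-up are included.

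**The median.** The mean is the most affected statistic, and the plan also reports the median and quartiles. In the base case the imputed median is right for four of five injections, and in the mixed short/long case it is right when pooled. This stands. It does not rescue the mean or the resolved-only durations.

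**Accuracy of the alternative.** With 72 participants (Protocol 1.2.2.2) and an assumed 10% reacting per injection, about 36 events (72 × 5 × 0.10), Kaplan-Meier removes the bias in the pooled median but adds variance. Root mean squared error, Kaplan-Meier against imputed, was about 46 to 47 against 40 to 41 days at a true median of 180, and 102 to 105 against 105 to 106 at 365. It is not a more accurate median at this size.

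**Importance.** A reader might take the protocol's amendment log as evidence that persistent ISRs were a recognised problem: "Section describing management of injection site reactions (ISRs) that are Grade 3 or higher, or persisting for more than 26 weeks has been removed". That section is superseded. The log ties it to borosilicate vial lots no longer in use and says enough safety data had been collected. It does not show how common persistence is.

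It is also fair that the imputation rule is explicit, that 7.1.7.2 names its events as resolved, and that percent ongoing is tabulated by PT and injection. This discloses the censoring. It does not correct the durations, and nothing marks the imputed values in 7.1.7.1.

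**Conclusion.** The point holds in limited form. The imputed mean is low by construction whenever an ongoing ISR outlasts its imputed date, and resolved-only durations favour short events. Neither direction depends on a distribution. Size does, and the documents supply no ISR durations: the effect is negligible at a true median of 30 days (mean 1% low) and substantial at 180 (18%) or 365 (38%), under the stated assumptions of exponential durations, nominal injection dates and no dropout. The apparent fall in duration from 173 to 83 days across five injections rests on the same assumptions and on reading 7.1.7.2 as a per-injection summary. The imputed median is distorted mainly for long-lasting reactions and the latest injections.

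No test or decision rule uses these statistics, so the effect is on description only. It is worth correcting before the Year 2 and Year 3 tables are produced, but it threatens no efficacy or safety conclusion that the plan defines.

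**What to change.** - For each PT, at least nodule and induration, report the overall Kaplan-Meier median and quartiles of duration, censoring ongoing ISRs at the date 7.1.7.1 already defines.
- Add the Kaplan-Meier proportion still present at 26 and 52 weeks. Give it per injection only where actual follow-up at the cut allows. Do not assume a minimum cut of Day 778: a Day 688 cut leaves 124 days for Week 78 (under 182) and 306 for Week 52 (under 364).
- Do not report a mean that includes imputed durations unless it is marked as a lower bound.
- Keep the resolved-only durations, labelled as such, beside percent ongoing.
- Flag imputed durations as minimum values in the listings.
- If intervals are given, allow for repeated ISRs within a participant, for example by participant-level bootstrap.

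**Cost.** SAP wording and a little programming on dates already collected. The Kaplan-Meier median is more variable than the imputed median when events are few (root mean squared error about equal at roughly 36 events). Some quartiles will not be estimable: in the feasibility runs Q3 could be estimated in 99.7% of simulated trials at a true median of 180 and in 78% at 365. Kaplan-Meier also assumes that leaving the study is unrelated to ISR duration, so ISRs ongoing at discontinuation should be counted separately.

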#### 7.1.7.2. Selected Study Drug Related ISRs

Selected study drug related ISRs include study drug related injection site induration, nodule, swelling, erythema, and pain.

The number and percentage of participants who experienced at least 1 selected study drug related ISR will be provided and summarized by SOC, PT and severity for each SC injection and the overall.

For each PT term of the study drug related ISRs, percentage of ongoing and resolved events will be summarized for each SC injection (Day 1 SC, Week 26, Week 52, etc.) and the overall at both participant-level and event-level.

For the participant-level summary, if a participant had more than one events of the same PT term, the participant will be counted in the “Ongoing” category unless all events of that same PT term have been resolved.

For the event-level summary, duration of the resolved events will also be summarized using descriptive statistics.

A by-participant listing for study drug related injection site induration and nodules and the corresponding duration will be provided.

## 7.2. Laboratory Evaluations

Laboratory data collected during the study will be analyzed and summarized using both quantitative and qualitative methods. Summaries of laboratory data will be provided for the Safety Analysis Set and will include all available data at the time of the database snapshot for the interim analysis. The analysis will be based on values reported in conventional units. When values are below the LOQ, they will be listed as such, and the closest imputed value will be used for the purpose of calculating summary statistics as specified in Section 3.7 Hemolyzed test results will not be included in the analysis, but they will be listed in by-participant laboratory listings.

## Calcium Corrected for Albumin

Calcium corrected for albumin will be calculated and summarized for the study. The following formula will be used when both serum calcium and albumin results for a given blood drawn are available and serum albumin value is < 4.0 g/dL.

$$\text{Calcium corrected for albumin (mg/dL)} = \text{serum calcium (mg/dL)} + 0.8 \times (4.0 - \text{albumin (g/dL)})$$

Toxicity grading for calcium will be applied based on the corrected values.

## Estimated Glomerular Filtration Rate

The following formulae will be used to calculate the estimated glomerular filtration rate using Cockcroft-Gault formula (eGFRCG):

$$\text{eGFR}_{\text{CG}} \text{ (mL/min)} = [(140 - \text{age (yrs)}) \times \text{weight (kg)} \times (0.85 \text{ if female})] / (\text{SCr (mg/dL)} \times 72),$$

where weight is total body mass in kilograms and SCr is serum creatinine.

A by-participant listing for laboratory test results will be provided by participant ID number and visit in chronological order for hematology, (urine) chemistry, and urinalysis separately. Values falling outside of the relevant reference range and/or having a severity grade of 1 or higher based on Division of AIDS (DAIDS) Table for Grading the Severity of Adult and Pediatric Adverse Events, Version 2.1 dated July 2017, will be flagged in the data listings, as appropriate.

No formal statistical testing is planned.

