4.2. Inclusion Criteria

Participants must meet all of the following inclusion criteria to be eligible for participation in this study:

- 1) Willing and able to provide written informed consent (participants ≥ 18 years of age) and assent (participants ≥ 12 and < 18 years of age) prior to performing study procedures. For participants ≥ 12 and < 18 years of age, parent or legal guardian willing and able to provide written informed consent prior to performing study procedures as required by local law.
- 2) Adult aged ≥ 18 years (at all sites) or adolescent aged ≥ 12 and weighing ≥ 35 kg (at sites in North America and Dominican Republic).
- 3) Are receiving a stable failing ARV regimen for > 8 weeks before screening and willing to continue the regimen until Day 1. Participants in Cohort 1 must also be willing to continue the failing regimen until completing the Functional Monotherapy Period (Day 1 to Day 14).
- 4) Have HIV-1 RNA ≥ 400 copies/mL at screening.
- 5) Have screening or available historical HIV resistance reports showing resistance to ≥ 2 ARV medications from each of ≥ 3 of the 4 main classes of ARV medications (NRTI, nonnucleoside reverse transcriptase inhibitor [NNRTI], protease inhibitor [PI], INSTI). Resistance to FTC or lamivudine (3TC) associated with the presence of the M184V/I reverse transcriptase (RT) mutation cannot be used for the purpose of determining this eligibility criterion.
- 6) Have ≤ 2 fully active ARV remaining from the 4 main classes that can be effectively combined to form a viable regimen in the opinion of the investigator based on resistance, tolerability, contraindication, safety, drug access, or acceptability to the participant. Refer to [Table 4](#) for list of disallowed ARVs.
- 7) Able and willing to receive an OBR together with LEN. Participants with an OBR without a fully active agent may be enrolled if the investigator considers that there is a favorable risk-benefit ratio for the participant. With prior approval from Gilead, components of the OBR may be investigational (ie, not yet approved).
- 8) A negative serum pregnancy test is required for all women at screening.

- 9) Participants of childbearing potential who engage in heterosexual intercourse must agree to use protocol-specified method(s) of contraception as described in [Appendix 4.](#)
- 10) Lactating women must agree to discontinue nursing before administration of LEN.

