6.5.1. Blood Samples

Blood sample collection for the following laboratory analyses will be performed at every visit, unless specified:

- Serum pregnancy test for all women (screening visit only).
- Serum follicle-stimulating hormone (FSH) test (FSH test is required for women who are < 54 years old and have stopped menstruating for ≥ 12 months but do not have documentation of ovarian hormonal failure) (screening visit only).
- Chemistry profile: alkaline phosphatase, aspartate aminotransferase, ALT, gamma-glutamyl transferase, total bilirubin, direct and indirect bilirubin, total protein, albumin, lactate dehydrogenase, creatine kinase (CK), bicarbonate, blood urea nitrogen, calcium, chloride, creatinine, glucose, lipase, magnesium, phosphorus, potassium, sodium, uric acid (except at the Cohort Selection, Days 2, 5, 16, and 19 visits).
- Estimated GFR (except at the Cohort Selection, Days 2, 5, 16, and 19 visits) according to:
 - Cockcroft-Gault formula for CL_{cr} for participants ≥ 18 years of age.
Men:
$$\frac{(140 - \text{age in years}) \times (\text{wt in kg})}{72 \times (\text{serum creatinine in mg/dL})} = CL_{cr} \text{ (mL/min)}$$

Women:
$$\frac{(140 - \text{age in years}) \times (\text{wt in kg}) \times 0.85}{72 \times (\text{serum creatinine in mg/dL})} = CL_{cr} \text{ (mL/min)}$$
 - Schwartz Formula for participants < 18 years of age.
Adolescent boys ≥ 12 years of age: $0.70 \times L/S_{Cr}$ (L is height in cm).
Adolescent girls ≥ 12 years of age: $0.55 \times L/S_{Cr}$ (L is height in cm).
- Hematology profile: complete blood count with differential and platelet count (except at the Cohort Selection visit, Days 2, 5, 16, and 19 visits).
- CD4+ cell count (except at the Cohort Selection visit, Days 2, 5, 16, and 19 visits).

- Plasma HIV-1 RNA (except at Day 5 and 19).
- HIV-1 genotype and phenotype for protease (PR), RT, integrase (IN), and capsid at screening visit and any subsequent visit with virologic failure (described in Section 6.7).
- HBV serologies (HBV surface antigen, HBV core antibody, HBV surface antibody) (screening only).
- HCV antibody serology (screening only).
- Optional pharmacogenomics testing (Day 1 only, if additional consent for pharmacogenomics testing is obtained and it may be collected at any time during the study).
- Plasma storage samples for optional safety and virology testing (HIV-1 genotype and phenotype) (except at Day 5 and 19).

PK Sampling

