### 7.2.1. Summaries of Numeric Laboratory Results

Descriptive statistics will be provided by treatment group for white blood cells, neutrophils (absolute result and %), lymphocytes (absolute result and %), creatinine, estimated glomerular filtration rate (eGFR) by CG, albumin, alkaline phosphatase, alanine amino transferase (ALT), aspartate amino transferase (AST), total bilirubin as follows:

- Baseline values
- Values at each postbaseline visit
- Change from baseline at each postbaseline visit

A baseline laboratory value will be defined as the last measurement obtained on or prior to the date of first dose of study drug. Change from baseline to a postbaseline visit will be defined as the visit value minus the baseline value. The mean, median, Q1, Q3, minimum, and maximum values will be displayed to the reported number of digits; SD values will be displayed to the reported number of digits plus 1.

Median (Q1, Q3) of the change from baseline values for the above laboratory tests (except for % neutrophils and lymphocytes) will be plotted using a line plot by cohort and treatment group and visit.

In the case of multiple values in an analysis window, data will be selected for analysis as described in Section 3.8.3.

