## **7.8. Changes from Protocol-Specified Safety Analyses**

No change from protocol-specified safety analyses is planned.

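### SAP eGFR uses Cockcroft-Gault with no age limit, whereas the protocol sets Schwartz under 18, so any adolescents' values would not follow the protocol's definition

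*SAP*

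**What the plan says.** Protocol 4.2 (criterion 2) admits adults at all sites and, at sites in North America and the Dominican Republic, an "adolescent aged ≥ 12 and weighing ≥ 35 kg".

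Protocol 6.5.1 defines estimated GFR by age. It sets "Cockcroft-Gault formula for CL_{cr} for participants ≥ 18 years of age" and "Schwartz Formula for participants < 18 years of age". The Schwartz value is height in cm divided by serum creatinine, times 0.70 for boys and 0.55 for girls. Exclusion criterion 12a in Protocol 4.3 applies the same age split to the entry limit. Estimated GFR is not taken at Cohort Selection or on Days 2, 5, 16 and 19.

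SAP 7.2 states: "The following formulae will be used to calculate the estimated glomerular filtration rate using Cockcroft-Gault formula". The single formula that follows uses age, total body weight, serum creatinine and a factor of 0.85 for females, with no age condition. SAP 7.2.1 lists "creatinine, estimated glomerular filtration rate (eGFR) by CG, albumin" among the variables summarised at baseline, at each later visit and as change from baseline, with a line plot of the median and quartiles of change. The Safety Analysis Set (SAP 3.1.3) has no age restriction. The Schwartz formula appears nowhere in the SAP. SAP 7.8 says: "No change from protocol-specified safety analyses is planned".

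**The concern.** Read together, the two documents give different eGFR values for the same participant under 18. A programmer who follows the SAP would apply the adult formula to every record. That adolescent's baseline would then differ from the value the protocol used at screening. Change from baseline would also respond to body weight, which Schwartz does not use. At stake is whether the renal summaries, the change plots and any listing built on this variable follow the protocol's own definition for adolescents, and whether a reader is told if they do not.

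**Working it through.** **Inputs.** The documents give no eGFR value, so there is no figure of the plan's own to reproduce. The formulas come from Protocol 6.5.1 and SAP 7.2. Ages, weights, heights and creatinine values below are assumptions, chosen within the eligibility limits (12 years and over, 35 kg and over).

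**Formulas** (CG = Cockcroft-Gault, SCr = serum creatinine in mg/dL)

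- CG = (140 − age) × weight / (72 × SCr), × 0.85 if female
- Schwartz = 0.70 × height / SCr for boys, 0.55 × height / SCr for girls

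Creatinine cancels in the ratio of the two:

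- Boys: CG / Schwartz = (140 − age) × weight / (50.4 × height), since 72 × 0.70 = 50.4
- Girls: CG / Schwartz = 0.85 × (140 − age) × weight / (39.6 × height), since 72 × 0.55 = 39.6

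**Results for assumed profiles** (mL/min)

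| Profile | SCr | CG (SAP) | Schwartz (protocol) | Ratio |
|---|---|---|---|---|
| Boy 12 y, 35 kg, 145 cm | 0.6 | 103.7 | 169.2 | 0.61 |
| Girl 12 y, 35 kg, 145 cm | 0.6 | 88.1 | 132.9 | 0.66 |
| Boy 15 y, 55 kg, 168 cm | 0.8 | 119.4 | 147.0 | 0.81 |
| Girl 15 y, 52 kg, 160 cm | 0.7 | 109.6 | 125.7 | 0.87 |
| Boy 17 y, 65 kg, 175 cm | 0.9 | 123.4 | 136.1 | 0.91 |
| Girl 17 y, 57 kg, 163 cm | 0.7 | 118.2 | 128.1 | 0.92 |
| Boy 17 y, 95 kg, 175 cm | 0.9 | 180.3 | 136.1 | 1.32 |
| Girl 17 y, 90 kg, 163 cm | 0.7 | 186.7 | 128.1 | 1.46 |

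**Direction.** The formulas agree only at one weight for a given age, sex and height. For a 15-year-old boy of 168 cm it is 50.4 × 168 / 125 = 67.7 kg. For a 15-year-old girl of 160 cm it is 39.6 × 160 / (0.85 × 125) = 59.6 kg. Below that weight CG is lower than Schwartz; above it CG is higher.

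**Effect of growth.** SAP 3.7 derives age at the date of each measurement, and the protocol schedules weight at most visits. Assume a boy goes from 50 kg at 14 to 60 kg at 16 with unchanged creatinine. CG changes by (124 × 60) / (126 × 50) − 1 = 7440 / 6300 − 1 = +18%, with no change in creatinine.

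**How far apart near 50 mL/min.** An assumed girl of 12 years, 35 kg and 145 cm with SCr 1.1 has CG = 128 × 35 × 0.85 / (72 × 1.1) = 48.1 and Schwartz = 0.55 × 145 / 1.1 = 72.5. The two values lie on opposite sides of the limit in exclusion criterion 12a.

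**The case against.** The strongest objection is that the effect may be empty. The documents allow participants under 18 but never say that any were enrolled. The SAP was written with 72 participants in the study (Protocol 1.2.2.2) and splits its age subgroups only at 50. This does not show that there were no adolescents, but an actual error cannot be demonstrated. That stands, and the point is conditional for this reason.

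The variable is openly labelled as Cockcroft-Gault, and serum creatinine is summarised beside it. Both are true, and both limit the harm. The label still does not tell a reader that values under 18 depart from the protocol's method.

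A reader might infer that SAP 7.8 is false. The documents do not support that plainly. Protocol 8.6.3, the laboratory analysis section, refers only to selected laboratory data and names no eGFR formula; the age split sits in the assessment and eligibility sections. The fair statement is that the difference is not mentioned.

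A reader might also infer that Cockcroft-Gault understates renal function in adolescents. The heavier profiles above reverse the sign. Nor is anyone's eligibility put in doubt: it was settled at screening under the protocol, and the SAP does not recompute it.

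The SAP is based on Amendment 4, and the protocol supplied is Amendment 5. The log of key changes for Amendment 5 lists none to estimated GFR, so nothing there suggests that the age split is new.

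Finally, Schwartz has its own weakness here. Protocol Appendix 2 schedules height at screening only, so later values in a growing adolescent would rest on an outdated height. This stands and shapes the fix.

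**Conclusion.** The mismatch is real and goes unmentioned in the SAP. As written, the SAP would give any participant under 18 an eGFR that does not follow the protocol's definition. With the assumed profiles the SAP value is about 0.6 to 1.5 times the protocol value, in either direction, and ordinary weight gain moves it without any change in creatinine.

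The consequence rests on one unstated fact: that someone under 18 was enrolled and measured before turning 18. If there were few such participants, pooled medians and quartiles would move little. The affected output is descriptive, with no formal testing. The primary and secondary endpoints, the sample size and the data monitoring committee's enrolment rule do not use eGFR. This is a minor consistency point, worth correcting because it is cheap.

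**What to change.** In SAP 7.2 and 7.2.1:

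- Restrict the Cockcroft-Gault summaries and plots to records at age 18 or over at measurement.
- List eGFR for records under 18 separately, by the protocol's Schwartz formula (0.70 × height / SCr for boys, 0.55 × height / SCr for girls).
- State that screening height is used unless a later height exists.
- State that change from baseline is not computed across the two formulas for a participant who turns 18 on study. SAP 3.7 imputes the birth date as 1 July, so the switch date is approximate; say that the derived age governs.

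If Cockcroft-Gault at all ages is intended, declare that in SAP 7.8 instead. If no participant under 18 was enrolled, say so in SAP 7.2 and make no other change.

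The cost is a few sentences, one programming condition and a listing that may be short or empty. Participants who cross 18 lose change-from-baseline values after the switch, and Schwartz values at later visits stay limited by the screening-only height. Only descriptive safety output changes.
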